6.2. Clinical Laboratory Tests

Descriptive statistics (N, mean, median, minimum, and maximum) for values and changes from baseline will be provided for clinical laboratory tests (hematology, chemistry and urinalysis) at each scheduled time point in the IND and OP/MA phases. Baseline values (as described in Section 2.2) will be used for change summaries and to determine abnormal values during all treatment phases.

Clinical laboratory tests that meet the criteria for markedly abnormal will be listed by subject for each phase. The incidence of treatment-emergent markedly abnormal (TEMA) laboratory values that occurred at any time during each treatment phase will be presented. Clinical laboratory test values will be considered “TEMA using the criteria defined by the Sponsor (Janssen Research & Development, LLC)” listed in Attachment 1. The identification of TEMA laboratory values is based on the postbaseline value being out of range while the baseline value (defined above) is either missing or within the range given in Attachment 1. If postbaseline laboratory results are above the upper limit and the baseline value is below the lower limit, then the post-baseline abnormality will also be considered TEMA. The same applies to the postbaseline value being below the lower limit with the baseline value being above the upper limit. Baseline values are defined in Section 2.2.

The incidence of subjects with ALT values $> 3 \times$ upper normal limit (ULN) will be presented for each study phase. Additionally, incidence of hepatic toxicity (Hy’s Law)⁹ defined as ALT values $> 3 \times$ ULN and total bilirubin values $> 2 \times$ ULN will be presented for each study phase. Similar to the markedly abnormal analysis, only subjects with Baseline ALT values $\leq 3 \times$ ULN (and Baseline total bilirubin values $\leq 2 \times$ ULN for hepatic toxicity) (or if the Baseline value is missing) will be eligible for these analyses.

6.3. Vital Signs, Weight, and BMI

Descriptive statistics for values and changes from Baseline values (described in Section 2.2) at each scheduled time-point during the induction and optimization/maintenance phases will be presented for temperature, systolic blood pressure, diastolic blood pressure, pulse rate, respiratory rate, oxygen saturation, weight, and BMI. Baseline will be used for change summaries and to determine abnormal values during all treatment phases (IND and OP/MA). Graphical presentations will be provided.

In addition, descriptive statistics of pulse rate and blood pressure (systolic and diastolic) values and changes and percent changes from predose will be provided for each intranasal dosing day.

The proportion of subjects who have a treatment-emergent abnormality, as defined in Table 4 below, during each treatment phase will be presented. A listing of subjects meeting any of the following criteria during each treatment phase will also be provided.

Table 4: Treatment-Emergent Abnormality Categories for Vital Signs

Vital Parameter	Post-baseline value outside of normal limit if:	
	Abnormally low	Abnormally high
Pulse (bpm)	A decrease from Baseline of ≥ 15 to a value ≤ 50	An increase from Baseline of ≥ 15 to a value ≥ 100
Systolic BP (mmHg)	A decrease from Baseline of ≥ 20 to a value ≤ 90	An increase from Baseline of ≥ 20 to a value ≥ 180
Diastolic BP (mmHg)	A decrease from Baseline of ≥ 15 to a value ≤ 50	An increase from Baseline of ≥ 15 to a value ≥ 105

BP = blood pressure; Baseline is defined in Section 2.2.

The proportion of subjects who experienced treatment-emergent acute hypertension (systolic BP ≥ 180 or diastolic BP ≥ 110) at any time during each treatment phase will be summarized by hypertension status.

Mean (+/-SE) values for systolic BP, diastolic BP and heart rate will be summarized by hypertension status and presented graphically for each treatment phase. In addition, for subjects with hypertension who receive antihypertensive medication, the same tables and graphs will be summarized by medication type (beta-blockers, all other agents).

A listing of subjects with oxygen saturation less than 93% will be provided.

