2.1.2. Endpoints

Safety endpoints are listed below.

- Occurrence of TEAEs, including TEAEs of special interest
- Potential short-term effects observed on the day of intranasal treatment session with special attention to changes from baseline/predose over time for:
 - Blood pressure (systolic and diastolic) and heart rate
 - Blood oxygen saturation
 - 12-lead electrocardiogram
 - Alertness and sedation using Modified Observer's Assessment of Alertness/Sedation (MOAA/S)
- Long-term effects, with special attention to changes from baseline over time for:
 - Computerized cognitive battery and Hopkins Verbal Learning Test-Revised (HVLT-R), to assess potential effects on cognitive function
 - Columbia-Suicide Severity Rating Scale (C-SSRS), to assess potential effects on suicidal ideation and behavior
- Changes from baseline over time in clinical laboratory tests, including hematology, serum chemistry, and urinalysis
- Time to discharge readiness, using the Clinical Global Assessment of Discharge Readiness (CGADR)

Efficacy endpoints include changes from baseline over time for the following:

- Depressive symptoms, including response ($\geq 50\%$ improvement from baseline) and remission (MADRS total score ≤ 12 , PHQ-9 total score < 5); using the Montgomery Asberg Depression Rating scale (MADRS) and 9-item self-reported Patient Health Questionnaire (PHQ-9)
- Overall severity of illness, using the Clinical Global Impression Severity (CGI-S)

- Functioning and associated disability, using the Sheehan Disability Scale (SDS)
- Health related quality of life and health status, using the European Quality of Life (EuroQol) Group, 5-Dimension, 5-Level (EQ-5D-5L)
- Health related quality of life using the Quality of Life in Depression Scale (QLDS)

Exploratory endpoints include:

- Changes from baseline over time for:
 - Depression response and remission rates (as defined above) to a second induction phase in eligible subjects who had relapsed in study ESKETINTRD3003, assessed using the MADRS and PHQ-9
 - Subject treatment satisfaction
- Subject tradeoff preferences for key benefit and harm outcomes associated with TRD treatment, using a stated-choice preference survey

Refer to Section 9, Study Evaluations for evaluations related to endpoints.

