1.1. Trial Objectives

Primary Objectives

The primary objective of this study is to assess the safety and tolerability of intranasal esketamine in subjects with Treatment Resistant Depression (TRD), with special attention to the following:

- Potential long term effects on cognitive function
- Treatment-emergent adverse events (TEAEs), including TEAEs of special interest
- Post dose effects on heart rate, blood pressure, respiratory rate and blood oxygen saturation
- Potential effects on suicidal ideation/behavior

Secondary Objective

The secondary objective is to assess long-term efficacy, including effects on:

- Depressive symptoms (clinician and self-reported),
- Overall severity of depressive illness,
- Functioning and associated disability,
- Health-related quality of life and health status,

Exploratory Objectives

The exploratory objectives are to assess:

- Medical resource utilization
- Response and remission rates to a second induction phase in eligible subjects who had relapsed in study ESKETINTRD3003
- Subject treatment satisfaction
- Subject tradeoff preferences for key benefit and harm outcomes associated with TRD treatment, using a stated-choice preference survey

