2.1.2. Analysis Phase Start and End Dates

Induction Phase

The start date of the induction phase (referred to as, 'IND start date') is the date of the first dose of intranasal study medication in the induction phase. For subjects who continue to the optimization/maintenance phase, the induction phase end date (referred to as, 'IND end date') is the date of first dose of intranasal study medication taken in the optimization/maintenance phase or the date of the last visit in the induction phase if date of the first dose is missing. For subjects who discontinue in the induction phase, IND end date is the maximum of the date of the last visit in the induction phase or the date of early termination from the induction phase.

The start date/time of the induction phase (referred to as, 'IND start date/time') is the IND start date and the time of the first dose of intranasal study medication in this phase. If no intranasal study medication is administered, the time will be left blank.

The start and end dates for the induction phase are only defined for subjects who enter the study at the induction phase.

Optimization/Maintenance Phase

The start date of the optimization/maintenance phase (referred to as, 'OP/MA start date') is the OP/MA start date of the first dose of intranasal study medication in this phase. For subjects who complete/discontinue from the optimization/maintenance phase, the phase end date (referred to as, 'OP/MA end date') is the maximum of the date of the last visit in the optimization/maintenance phase or the date of completion/withdrawal from the optimization/maintenance phase.

The start date/time of the optimization/maintenance phase (referred to as, 'OP/MA start date/time') is the OP/MA start date and the time of the first dose of intranasal study medication in this phase.

Follow-Up Phase

The start date of the follow-up (post-treatment) phase (referred to as, 'F/U start date') is the day after the end date of the last treatment phase in which the subject participated. For subjects who complete/discontinue from the follow-up phase, the follow-up phase end date (referred to as, 'F/U end date') is the maximum of the last follow-up visit date or end of trial date.

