2.2. Baseline and End Point

Baseline is defined for each parameter/assessment.

- Study Baseline: For subjects who enter the study at the induction phase, the last observation prior to or on the start date of induction phase is denoted as 'Baseline'; for subjects who directly enter the study at the optimization/maintenance phase, the last observation prior to or on the start date of optimization/maintenance phase is denoted as 'Baseline'.
- Baseline (OP/MA): The last observation prior to or on the start date of the optimization/maintenance phase is denoted as 'Baseline (OP/MA)'.

Note:

- The 'Study Baseline' value is used to describe the change from baseline in the safety analysis unless otherwise specified.
- For subjects who enter the study at the induction phase, the 'Baseline (IND)' value is used for the efficacy analysis for the induction phase.; for subjects who enter the optimization/maintenance phase, the 'Baseline (OP/MA)' is used for the efficacy analysis for the optimization/maintenance phase.

For each variable measured over time, the 'End Point (IND)' value is defined as the last postbaseline assessment value during the induction phase for subjects who enter the study at the induction phase.

The ‘End Point (OP/MA)’ value is defined as the last postbaseline assessment value during the optimization/maintenance phase.

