		22 + i*14	Week (4 + i*2) (OP/MA)	16 + i*14 to 29 + i*14	22 + i*14
OP/MA final visit	End Point (OP/MA)	2 to end of OP/MA			
Patient Health Questionnaire – 9 item (PHQ-9), EuroQol Group; 5 dimension; 5 level (EQ-5D-5L), Quality of Life in Depression Scale (QLDS)	IND	1	Baseline	≤ 1	1
		15	Day 15 (IND)	2 - 21	15
		28	Day 28 (IND)	22 to end of IND	28
	IND final visit	End Point (IND)	2 to end of IND		
	OP/MA i=1,2,3,...	1	Baseline (OP/MA)	≤ 1	1
		15	Week 3 (OP/MA)	2 - 32	15
		50	Week 8 (OP/MA)	33 - 64	50
		50 + i*28	Week (8 + i*4) (OP/MA)	37 + i*28 to 64 + i*28	50 + i*28
OP/MA final visit	End Point (OP/MA)	2 to end of OP/MA			
Sheehan Disability Scale (SDS)	IND	1	Baseline	≤ 1	1
		28	Day 28 (IND)	2 to end of IND	28
		IND final visit	End Point (IND)	2 to end of IND	
	OP/MA i=1,2,3,...	1	Baseline (OP/MA)	≤ 1	1
		15	Week 3 (OP/MA)	2 - 32	15
		50	Week 8 (OP/MA)	33 - 64	50
		50 + i*28	Week (8 + i*4) (OP/MA)	37 + i*28 to 64 + i*28	50 + i*28
	OP/MA final visit	End Point (OP/MA)	2 to end of OP/MA		
Treatment Satisfaction Questionnaire for Medication (TSQM-9)	IND	1	Baseline	≤ 1	1
		28	Day 28 (IND)	2 to end of IND	28
		IND final visit	End Point (IND)	2 to end of IND	
	OP/MA i=1,2,3,...	1	Baseline (OP/MA)	≤ 1	1
		50	Week 8 (OP/MA)	2 - 64	50
		50 + i*28	Week (8 + i*4) (OP/MA)	37 + i*28 to 64 + i*28	50 + i*28
OP/MA final visit	End Point (OP/MA)	2 to end of OP/MA			
	IND	28	Day 28 (IND)	1 to end of IND	28

Table 1: Analysis Visits

Parameter	Analysis Phase	Scheduled Day ^a	Time Interval (label on output)	Time Interval ^a (Day)	Target Time Point ^a (Day)
Patient Stated-choice Preference	OP/MA	22	Week 4 (OP/MA)	1 to end of OP/MA	22
Nasal exam	IND	1	Baseline	≤ 1	1
		28	Day 28 (IND)	2 to end of IND	28
		IND final visit	End Point (IND)	2 to end of IND	
Vital Signs: Temperature (TEMP) (IND [predose], OP/MA [predose]), Blood Pressure (BP) ^b , Hear Rate (HR), Respiratory (RESP) (IND [predose, 40M, 1H, 1H30M], OP/MA [predose, 40M, 1H])	IND	1	Baseline	≤ 1 / predose	1
			Day 1 (IND): 40M		
			Day 1 (IND): 1H		
			Day 1 (IND): 1H30M		
		4	Day 4 (IND): Predose	2 - 6	4
			Day 4 (IND): 40M		
			Day 4 (IND): 1H		
			Day 4 (IND): 1H30M		
		8	Day 8 (IND): Predose	7 - 9	8
			Day 8 (IND): 40M		
			Day 8 (IND): 1H		
			Day 8 (IND): 1H30M		
		11	Day 11 (IND): Predose	10 - 13	11
			Day 11 (IND): 40M		
			Day 11 (IND): 1H		
			Day 11 (IND): 1H30M		
		15	Day 15 (IND): Predose	14 - 16	15
			Day 15 (IND): 40M		
			Day 15 (IND): 1H		
			Day 15 (IND): 1H30M		
		18	Day 18 (IND): Predose	17 - 20	18

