			Day 18 (IND): 40M		
			Day 18 (IND): 1H		
			Day 18 (IND): 1H30M		
		22	Day 22 (IND): Predose	21 - 23	22
			Day 22 (IND): 40M		
			Day 22 (IND): 1H		
			Day 22 (IND): 1H30M		
25	Day 25 (IND): Predose	24 to end of IND	25		
	Day 25 (IND): 40M				
	Day 25 (IND): 1H				
	Day 25 (IND): 1H30M				
IND final visit	IND final visit	End Point (IND)	Day 1 (IND): 40M to end of IND		

Table 1: Analysis Visits

Parameter	Analysis Phase	Scheduled Day ^a	Time Interval (label on output)	Time Interval ^a (Day)	Target Time Point ^a (Day)
	OP/MA i=1,2,3,...	1	Baseline (OP/MA)	≤ 1	1
			Week 1 (OP/MA): 40M		
			Week 1 (OP/MA): 1H		
		8	Week 2 (OP/MA): Predose	2 - 11	8
			Week 2 (OP/MA): 40M		
			Week 2 (OP/MA): 1H		
		15	Week 3 (OP/MA): Predose	12 - 18	15
			Week 3 (OP/MA): 40M		
			Week 3 (OP/MA): 1H		
		22	Week 4 (OP/MA): Predose	19 - 25	22
			Week 4 (OP/MA): 40M		
			Week 4 (OP/MA): 1H		
		22 + i*7	Week (4 + i*1) (OP/MA): Predose	19 + i*7 to 25 + i*7	22 + i*7
Week (4 + i*1) (OP/MA): 40M					
Week (4 + i*1) (OP/MA): 1H					
OP/MA final visit	End Point (OP/MA)	Week 1: 40M to end of OP/MA			
Weight and body mass index (BMI), Hematology and Chemistry, Urinalysis	IND	1	Baseline	≤ 1	1
		28	Day 28 (IND)	2 to end of IND	28
		IND final visit	End Point (IND)	2 to end of IND	
	OP/MA i=1,2,3,...	1	Baseline (OP/MA)	≤ 1	1
		106	Week 16 (OP/MA)	2 - 148	106
		106 + i*84	Week (16 + i*12) (OP/MA)	65 + i*84 to 148 + i*84	106 + i*84
		OP/MA final visit	End Point (OP/MA)	2 to end of OP/MA	
Electrocardiogram (ECG)	IND	1	Baseline	≤ 1 / predose	1
			Day 1 (IND): 1H		
		15	Day 15 (IND): 1H	2 - 20	15
		25	Day 25 (IND): 1H	21 to end of IND	25
	IND final visit	End Point (IND)	Day 1 (IND): 1H to end of IND		
	OP/MA i=1,2,3,...	1	Baseline (OP/MA)	≤ 1	1
			Week 1 (OP/MA): 1H		
		50	Week 8 (OP/MA): 1H	2 - 64	50
50 + i*28		Week (8 + i*4) (OP/MA): 1H	37 + i*28 to 64 + i*28	50 + i*28	

Table 1: Analysis Visits

Parameter	Analysis Phase	Scheduled Day ^a	Time Interval (label on output)	Time Interval ^a (Day)	Target Time Point ^a (Day)	
		OP/MA final visit	End Point (OP/MA)	Week 1: 1H to end of OP/MA		
Columbia-Suicide Severity Rating Scale(C-SSRS)	IND	1	Baseline	≤ 1	1	
		4	Day 4 (IND)	2 - 6	4	
		8	Day 8 (IND)	7 - 9	8	
		11	Day 11 (IND)	10 - 13	11	
		15	Day 15 (IND)	14 - 16	15	
		18	Day 18 (IND)	17 - 20	18	
		22	Day 22 (IND)	21 - 23	22	
		25	Day 25 (IND)	24 - 26	25	
		28	Day 28 (IND)	27 to end of IND	28	
	IND final visit	End Point (IND)	2 to end of IND			
	OP/MA i=1,2,3,...	1	Baseline (OP/MA)	≤ 1	1	

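### SAP 6.3 gives change from same-session predose for pulse and blood pressure only; respiratory rate and oxygen saturation lack it after the first-dose session, and the written SpO2 baseline is not tied to predose

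*SAP*

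**What the plan says.** SAP 1.1 and Protocol 2.1.1 list among the primary objectives "Post dose effects on heart rate, blood pressure, respiratory rate and blood oxygen saturation". Protocol 2.1.2 turns part of this into an endpoint: "Potential short-term effects observed on the day of intranasal treatment session with special attention to changes from baseline/predose over time for" blood pressure and heart rate, oxygen saturation, ECG and MOAA/S. Respiratory rate is in the objective but not in that endpoint list.

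SAP 6.3 summarises values and changes from Baseline at each scheduled time point for all vital signs, including respiratory rate and oxygen saturation. It then adds, for each dosing day, that "descriptive statistics of pulse rate and blood pressure (systolic and diastolic) values and changes and percent changes from predose will be provided". SAP 6.6.2 plans change from predose for MOAA/S. No section plans it for respiratory rate or SpO2. The other SpO2 output is a listing of subjects below 93%.

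For safety, SAP 2.2 uses Study Baseline. For induction entrants, "the last observation prior to or on the start date of induction phase is denoted as" Baseline; direct entrants to optimization/maintenance (OP/MA) have the matching rule for that phase. SAP 2.1.2 defines the induction start date as a date only: it "is the date of the first dose of intranasal study medication in the induction phase". A start date/time is defined separately. For OP/MA, for example, it "is the OP/MA start date and the time of the first dose of intranasal study medication in this phase". The baseline rule uses the date.

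**The concern.** A postdose effect is a change within a session. Change from Study Baseline equals that change only when the baseline is the predose reading of the same session. At later sessions it also contains whatever has shifted in the subject since study entry. Two of the four measures in the objective are therefore left without their direct summary, while the SAP supplies it for the other two and for MOAA/S.

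What is lost is the spread and the extremes of individual within-session changes. For SpO2 this matters for falls that stay at or above 93%. For respiratory rate there is no threshold at all, since SAP Table 4 sets limits for pulse and blood pressure only.

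The baseline wording is a separate, smaller problem. If it were programmed as written, the SpO2 reference could itself be a postdose value.

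**Working it through.** The documents give no figure to reproduce on this point: there is no hypothesis, sample size or SpO2 effect estimate. The check is a comparison of the texts, plus a count.

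**1. What change from Study Baseline measures.** For session k, with Study Baseline B:

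post_k − B = (post_k − pre_k) + (pre_k − B)

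The last term is zero in every subject only at the first-dose session, and only if B is that session's predose reading.

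**2. Coverage in induction.** Dosing is twice a week for 4 weeks: 2 × 4 = 8 sessions (Days 1, 4, 8, 11, 15, 18, 22, 25).

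- Respiratory rate. Table 1 gives the times as "Respiratory (RESP) (IND [predose, 40M, 1H, 1H30M], OP/MA [predose, 40M, 1H", so 3 postdose readings per session. 8 × 3 = 24; less Day 1's 3 leaves 21; 21/24 = 87.5% without a same-session change.
- SpO2. Protocol 9.2 has readings every 15 minutes to 1 hour: 60/15 = 4 per session. 8 × 4 = 32; less Day 1's 4 leaves 28; 28/32 = 87.5%. If baseline is not the predose reading, the count is 32 of 32.

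Both percentages are simply 7/8 of the sessions. They describe coverage, not bias.

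**3. OP/MA.** Induction entrants keep their induction Study Baseline, so no session has a same-session change. Direct entrants have Week 1 only, again provided baseline is predose. For induction entrants the nominal age of the baseline is 4 − 1 = 3 days at Day 4, 25 − 1 = 24 days at Day 25, and 28 − 1 = 27 days at Visit 2.1 (expected to coincide with Day 28). It grows after that. Table 1 has weekly windows for both measures after Week 4, although the current Time and Events Schedule has no pulse oximetry after Visit 2.4.

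**4. What can be recovered.** Mean(post) − mean(pre) gives the mean change when the same subjects have both readings. The spread does not follow, because Var(post − pre) = Var(post) + Var(pre) − 2 Cov(post, pre) and the covariance is not tabulated. Nor do the extremes.

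**5. Baseline rule in Table 1.**

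| | Day 1 baseline cell | Separate Day 1 postdose rows | End Point starts |
|---|---|---|---|
| Vital signs, IND | Day 1 or earlier, marked predose | 40 min, 1 h, 1.5 h | first Day 1 postdose row |
| ECG, IND | Day 1 or earlier, marked predose | 1 h | first Day 1 postdose row |
| Vital signs, OP/MA | Day 1 or earlier, predose not stated | 40 min, 1 h | first Week 1 postdose row |
| Pulse oximetry, IND | Day 1 or earlier, predose not stated | none | Day 2 |
| Pulse oximetry, OP/MA | Day 1 or earlier, labelled Week 1, predose not stated | none | Day 2 |

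The induction vital-sign End Point, for instance, runs from "Day 1 (IND): 40M to end of IND". For pulse oximetry nothing narrows the date rule of SAP 2.2. The last observation on the start date is then the last Day 1 reading, scheduled at 60 minutes. With B equal to that value, the 60-minute change is B − B = 0 for every subject whose last reading is the 60-minute one. Monitoring can run later if SpO2 is below 93%, in which case B is a later postdose reading.

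**The case against.** No protocol commitment is broken. The endpoint wording in Protocol 2.1.2 accepts either baseline or predose as the reference, respiratory rate is not in that list, and Protocol 11.3 asks only for change from baseline, which SAP 6.3 delivers. This is correct: the gap is against the primary objective, not against a promised analysis.

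Predose rows for respiratory rate at later sessions let a reader separate the mean shift since entry from the mean acute effect. That also stands, apart from missing readings, but it does not give the distribution of individual changes.

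The pulse-oximetry rows are not split by time on any day, and MOAA/S has the same compressed layout although SAP 6.6.2 uses predose. The missing word is therefore weak evidence that a postdose baseline is intended, and a programmer may well use predose. This is fair as to intent. The written rule still permits the other result.

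The clinical safety net is real. SpO2 below 93% is listed. Falls below 93% lasting more than 2 minutes and confirmed at another body site are adverse events. Any clinically relevant change must be recorded as an adverse event under Protocol 9.2. Protocol 1.1.2.3 reports no clinically meaningful change in blood oxygen in the Phase 2 study. All this limits the consequence, but it does not describe smaller SpO2 falls or the distribution of respiratory-rate changes.

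**Conclusion.** The concern holds. After the first-dose session, within-session change in respiratory rate and SpO2 is not summarised, although the primary objective asks for postdose effects on both. In induction this affects 7 of 8 sessions, and for induction entrants every OP/MA session with readings. Observed values, change from Study Baseline and plots remain, so mean effects can be approximated; their spread and extremes cannot.

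The SpO2 baseline is a defect of wording that can produce a wrong reference value if followed literally. The 32 of 32 count and the zero change at 60 minutes depend on that literal reading. No SpO2 effect size is assumed, and the distortion may be small. The point should be corrected because part of the primary safety objective lacks its direct summary and the correction needs no new data.

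**What to change.** - **SAP 6.3:** add respiratory rate and oxygen saturation to the change-from-predose summaries, for each dosing day on which they are collected.
- **SAP 2.2:** for measures repeated on dosing days, define baseline as the last observation before the first dose, using the phase start date/time already defined in SAP 2.1.2.
- **SAP Table 1:** mark three baseline cells as predose (pulse oximetry in IND and in OP/MA, vital signs in OP/MA). Give the Day 1 postdose SpO2 readings their own rows: 4 in IND (15, 30, 45, 60 minutes) + 2 in OP/MA (30, 60 minutes) = 6. Start the two SpO2 End Point windows at the first Day 1 postdose reading.

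The cost is one sentence, these table edits and two more parameters in an existing output. All readings are already collected, and study conduct does not change.
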